Study Design:	
This is a multicenter, double-blind, randomized, and placebo-controlled prospective Phase II clinical study, designed to evaluate LT3001 drug product versus placebo in subjects with AIS. Subjects who participate in this trial should be treated with standard of care of AIS therapies when appropriate.
 
Approximately 200 eligible subjects will be randomized centrally 1:1 to LT3001 drug product or placebo with the stratification factors. Randomization will be stratified according to age [REDACTED], baseline NIHSS [REDACTED], and time of AIS symptoms onset to the planned 1st IP [REDACTED]. The stratified randomization is to ensure similar risk distributions with regards to efficacy measures at baseline in the treatment groups.
 
[REDACTED]
 
Each eligible subject will [REDACTED]
 
The first dose of LT3001 drug product or placebo (1st IP) will be administered within 24 hours after stroke symptoms onset.
 
[REDACTED]
 
LT3001 drug product or placebo will be administered [REDACTED].
 
[REDACTED]
 
A Data Safety Monitoring Board (DSMB) will be formed to assess all data (including imaging data) of LT3001 drug product or placebo treatment. The DSMB will review safety and efficacy data when the thirtieth treated subject has completed study procedures on Day 7 or terminated the study before Day 7. The DSMB will meet after the data presentation and will issue recommendations relating to safety and study conduct. Unscheduled meetings will be recommended and initiated by the Sponsor or the Principal Investigators.
 
The participation for each subject is approximately 92 days from the Screening (Visit 1) to the last visit.

Selection of Subjects:	
Inclusion Criteria:
 

1. Subject has been diagnosed with AIS.

2. Subject or if applicable subject's legally acceptable representative/ legally designated representative consents to participation by signing the informed consent form after receiving full information about the study.
3. Subject [REDACTED] is aged 18 to 90 years (inclusive) [REDACTED]  
[REDACTED] is aged 18 to 80 years (inclusive) at the time of Screening (Visit 1).
4. Subject has an NIHSS of 4 to 25.
5. Subject [REDACTED] is able to receive the 1st IP within 24 hours after stroke symptoms onset.  
[REDACTED]

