### 9.3.1 Method of Study Treatment Assignment

Subjects will be randomly assigned to receive LT3001 drug product or placebo in a ratio of 1:1. The randomization will be stratified according to age [REDACTED], baseline NIHSS [REDACTED], and the time of AIS symptoms onset to the planned 1st IP [REDACTED]. The stratified randomization is to ensure similar risk distributions [REDACTED]

At Screening (Visit 1), [REDACTED] EDC system will assign a unique subject identification number to the subject known as the Subject Number. This number will be associated with the subject throughout the study. Every subject who signs an ICF (or has a LAR/, LDR or impartial witness sign the ICF on their behalf) must be entered into [REDACTED] EDC system regardless of eligibility in order to obtain a Subject Number.

The unblinded statistician will produce a Master Randomization list for the random assignment of subjects to each treatment [REDACTED] and a Kit Randomization list for the random assignment of kit numbers for labelling to each treatment.

Randomization Manager will receive the Master randomization list and the Kit randomization list [REDACTED].

The subjects will be centrally randomized at a study level.

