4.1. Brief Description

This is a multicenter, double-blind, randomized, and placebo-controlled prospective Phase II clinical study, designed to evaluate LT3001 drug product versus placebo in subjects with AIS. The study is planned to take place in multiple countries. Subjects who participate in this trial should be treated with standard of care of AIS therapies when appropriate.

Approximately 200 eligible subjects will be randomized centrally 1:1 to LT3001 drug product or placebo with the stratification factors. Randomization will be stratified according to age [REDACTED], baseline NIHSS [REDACTED], and time of AIS symptoms onset to the 1st IP [REDACTED]

[REDACTED]

[REDACTED]

Each eligible subject will [REDACTED] The first dose of LT3001 drug product or placebo (1st IP) will be administered within 24 hours after stroke symptoms onset. [REDACTED]

[REDACTED]

LT3001 drug product or placebo will be administered [REDACTED].

A Data Safety Monitoring Board (DSMB) will be formed to assess all data (including imaging data) of LT3001 drug product or placebo treatment. [REDACTED] The DSMB will review safety and efficacy data when the thirtieth treated subject has completed study procedures on Day 7 or terminated the study before Day 7. The DSMB will meet after the data presentation and will issue recommendations relating to safety and study conduct. Unscheduled meetings will be recommended and initiated by the Sponsor or the Principal Investigators. [REDACTED]

[REDACTED]

[figure not shown]
[REDACTED]

[REDACTED]

The participation for each subject is approximately 92 days from the Screening (Visit 1) to the last visit.

This document is confidential.

Study Design

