10.1. Efficacy Endpoints for mRS and NIHSS and Analysis

10.1.1. Analysis of functional outcome based on mRS assessments

All binary response variables defined on mRS assessments at the respective visits will be summarized with the number and percentage of subjects with and without response by treatment group considering observed data of ITT. The difference of the proportions based on observed data of ITT between the treatment groups with the corresponding 95% confidence intervals (CIs) will be presented for the defined time points.

Comparison between the treatment groups will be performed for the binary response variables using the Chi-square test at each defined timepoint separately and additionally

Additionally, the comparison between the treatment groups at each timepoint and overall will be performed for the binary response

The model will be performed for both categorizations of mRS, i.e., subjects with mRS ≤ 2 and subjects with mRS ≤ 1

This document is confidential.

The number and percentage of subjects in each score category of mRS will be presented for baseline and for the post-baseline time points [REDACTED] by treatment group for observed ITT population. A shift table will be presented by treatment with shifts from baseline to each defined post-baseline time point [REDACTED]

[REDACTED]

The [REDACTED] steps are described in section 10.1.3.

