10.2.6. Proportion of subjects with 90% reduction in hypoperfusion lesion [REDACTED]
[REDACTED] from Baseline:

The number and percentage of subjects showing 90% reduction in hypoperfusion lesion [REDACTED]
[REDACTED] will be summarized by treatment group. The difference of the
proportions between the treatment groups and the corresponding 95% CIs will be presented.
Comparisons between treatment groups will be made on the observed data using the Chi-square test
[REDACTED].

[REDACTED]

This document is confidential.

11. Safety

Safety analyses will be performed on the Safety population.

Safety will be assessed based on the incidence of AEs and changes in laboratory results, vital signs, and ECG parameters. For repeated safety assessments collected at scheduled time points, the last non-missing pre-dose value will be used as baseline, and the first non-missing value at each post-dose time points will be used in the analyses. However, all pre- and post-dose assessments including repeat assessments will be presented in data listings. Data collected at unscheduled visits will be included in data listings but will not be considered for analyses.

All safety summaries and analyses will be performed using observed data on the Safety population without imputation of any missing safety data.

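### The visible risk differences and 95% CIs for the binary efficacy endpoints are not adjusted for the three stratification factors; an adjusted estimate should be pre-specified as the main one

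*SAP*

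**What the plan says.** **Design.** SAP 4.1 states: "Approximately 200 eligible subjects will be randomized centrally 1:1 to LT3001 drug product or placebo with the stratification factors". The factors are age, baseline NIHSS and time from symptom onset to first dose (Protocol 9.3.1, SAP 4.1 and 4.4); their cut-offs are redacted. The protocol synopsis gives the purpose: "The stratified randomization is to ensure similar risk distributions with regards to efficacy measures at baseline in the treatment groups".

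**Effect estimate.** SAP 10.1.1 plans to present "The difference of the proportions based on observed data of ITT between the treatment groups with the corresponding 95% confidence intervals" for the mRS responder endpoints. SAP 10.1.2 does the same for the NIHSS responder endpoints, and SAP 10.2.6 gives a difference with 95% CI for the 90% reduction in hypoperfusion lesion. Protocol 13.3.1 gives the same kind of difference for the mRS and NIHSS responders. These sentences are complete, and none names a stratum or covariate.

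**Test.** SAP 10.1.1 says "Comparison between the treatment groups will be performed for the binary response variables using the Chi-square test at each defined timepoint separately"; the sentence then runs on with *and additionally*, after which the text is missing. In SAP 10.1.2 redactions follow both the name of the test and the word *additionally*. SAP 10.2.6 says "Comparisons between treatment groups will be made on the observed data using the Chi-square test", followed by a redaction.

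**Other analyses whose content cannot be read.** SAP 10.1.1 plans a second comparison at each timepoint and overall, and a model for mRS ≤2 and mRS ≤1. The synopsis names an RMLR model for NIHSS response. SAP 8.5 has comparative analyses that consider a redacted item. SAP 10.1.3 makes multiple imputation the primary approach for mRS and NIHSS, with the details redacted.

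**The concern.** Stratified randomization balances the arms on the stratification factors. If those factors predict outcome, the arm difference varies less from trial to trial than it would under simple randomization. The usual variance of a raw difference in proportions does not know this: it still counts the between-stratum variation that the design has removed. The interval is then wider than it needs to be, and a test built on the same variance rejects too seldom.

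The plan itself treats the factors as related to efficacy, since balancing efficacy risk is its stated reason for stratifying. The synopsis also adjusts the NIHSS score for baseline NIHSS by ANCOVA. The visible risk differences make no such use of the factors.

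Precision is at stake. The SAP calls all comparisons descriptive (8.1 and 10), so the estimates and their intervals carry the efficacy message. With about 100 subjects per arm those intervals are already wide.

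**Working it through.** **Inputs**
- About 200 subjects randomized 1:1, so about 100 per arm (SAP 4.1).
- Three stratification factors, cut-offs redacted. Assumed: two levels each, eight equally likely strata, permuted blocks of 4.
- The sample-size sections (Protocol 13.1, SAP 4.3) show no text, so there is no power figure to reproduce. Assumed: two-sided 5% to match the 95% CIs, and 40% control response (30–60% for interval width).
- Prognostic strength R², the share of outcome variance explained by the strata, is not given. It is varied from 0 to 0.27.

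**Step 1: raw interval.** Half-width = 1.96 × √(2p(1−p)/100). At p = 0.3, 0.4, 0.5 and 0.6 this gives 12.7, 13.6, 13.9 and 13.6 percentage points.

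**Step 2: approximate effect of stratification.** If stratum response rates have standard deviation SD, then R² = SD²/(p(1−p)), and the true variance of the difference is (1 − R²) times the raw one. With p = 0.4, p(1−p) = 0.24.
- SD 0.15: variance ratio (0.24 − 0.0225)/0.24 = 0.906. The stratified CI is 1 − √0.906 = 5% narrower. The plain test's actual level is 2(1 − Φ(1.96/√0.906)), about 4.0%.
- SD 0.20: variance ratio (0.24 − 0.04)/0.24 = 0.833. The CI is 9% narrower and the actual level is about 3.2%.

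As an equivalent sample size, 200/(1 − R²) is 211 at R² = 0.05, 222 at 0.10, 250 at 0.20 and 286 at 0.30.

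**Step 3: simulation.** 6000 trials per scenario with N = 200 and the assumptions above. The plain chi-square test and raw CI were compared with the Cochran–Mantel–Haenszel (CMH) test and the Mantel–Haenszel risk difference (Sato variance). Power is at a conditional odds ratio of 2.

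| R² | Raw CI width ÷ stratified | Type I error, chi-square | Type I error, CMH | Power, chi-square | Power, CMH |
|---|---|---|---|---|---|
| 0 | 1.00 | 5.0% | 5.0% | 69.2% | 67.5% |
| 0.04 | 1.02 | 4.5% | 4.7% | 67.1% | 66.6% |
| 0.12 | 1.06–1.07 | 3.9% | 4.8% | 58.9% | 62.0% |
| 0.18 | 1.11 | 3.2% | 5.0% | 52.5% | 58.5% |
| 0.27 | 1.17 | 2.4% | 4.9% | 42.0% | 53.2% |

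Power should be compared within a row only: a fixed odds ratio of 2 corresponds to a risk difference of 17.1 points in the first row and 12.4 in the last. Across all scenarios the raw CI covered 94.7–97.8% and the stratified CI 94.5–95.2%.

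**Step 4: in points.** At 40% response, the raw half-width of 13.6 would become about 13.6/1.02 = 13.3 at R² = 0.04, 13.6/1.11 = 12.3 at R² = 0.18, and 13.6/1.17 = 11.6 at R² = 0.27.

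**The case against.** A reader might infer that the binary endpoints are compared by a plain chi-square test and nothing else, so that the strata are ignored. The documents do not support that. The SAP 10.1.1 sentence runs on into missing text, and in SAP 10.1.2 and 10.2.6 a redaction stands directly after the name of the test, where a qualifier could be. A further comparison and a model are planned with terms that cannot be read, and that model may already contain the three factors. Text lost to redaction is not missing from the plan. This part of the objection stands.

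A reader might also infer that the 95% CI is invalid. It is not invalid in the harmful direction: it over-covers, and the chi-square test rejects too seldom. The raw difference remains an unbiased estimate of the marginal effect and is a legitimate descriptive summary.

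Two further points stand. These endpoints are secondary: the primary endpoint is related adverse events, all comparisons are labelled descriptive, and the main approach for mRS and NIHSS rests on multiple imputation, not on the observed-data summary. And the gain may be nil: with R² up to about 0.04 the width changes by 2% at most and CMH has no more power.

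The objection does not remove the complete sentences on the difference and its CI, which show no adjustment. A hidden model may well be adjusted, but if it reports odds ratios, the only absolute difference the reader sees is still the raw one. Comparisons within subgroups of the stratification variables do not supply an adjusted overall difference either.

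**Conclusion.** The point holds in a limited form. For the binary mRS and NIHSS endpoints and the 90% hypoperfusion reduction, the visible risk difference and its 95% CI are unadjusted for the factors used in randomization. If those factors are prognostic, precision is lost and the error is conservative.

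Over the range examined, the loss runs from nothing to 17% of the stratified interval's width. Where in that range the trial falls cannot be settled from the documents, since cut-offs, response rates and prognostic strength are not visible. The figures also assume eight equal strata and complete data.

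Whether the plan as a whole ignores the strata cannot be determined from the visible text. No confirmatory decision depends on the point. It is an inexpensive gain in precision and does not rescue a faulty analysis.

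**What to change.** 1. Confirm whether the additional comparison and the model in SAP 10.1.1 and 10.1.2, and the test in 10.2.6, include age, baseline NIHSS and onset-to-first-dose time.
2. Pre-specify a stratum-adjusted risk difference with 95% CI as the main estimate for these endpoints. Either a Mantel–Haenszel difference over the randomization strata or a difference standardised from a logistic model with the three factors will do. Name one: a logistic odds ratio alone is a different quantity and does not replace the risk difference. For mRS and NIHSS, state how it is combined across imputed data sets.
3. Keep the raw difference and the chi-square test as supportive.
4. Fix a rule for pooling sparse strata before unblinding. Three factors make at least eight strata in about 200 subjects.

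**Cost:** SAP wording, standard software and a little more analysis work; no new data. If the strata prove weakly prognostic, there is little or no gain.

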10.1.2. Analysis of neurological outcome based on NIHSS assessments

All binary response variables defined on NIHSS assessments at the respective visits will be summarized with the number and percentage of subjects with and without response by treatment group considering observed data of ITT. The difference of the proportions based on observed data of ITT between the treatment groups with the corresponding 95% CIs will be presented for the defined time points.

Comparison between the treatment groups will be performed for the defined binary response variables using the Chi-square test [REDACTED] at each defined timepoint separately and additionally, [REDACTED]

[REDACTED]

Additionally, the comparison between the treatment groups at each timepoint and overall will be performed for the binary response variables [REDACTED]

[figure not shown]
[REDACTED]

The total score, subscores and change from baseline in NIHSS will be summarized at each defined time point by treatment group and overall on observed data of ITT [REDACTED]

[REDACTED]

This document is confidential.

Comparison between the treatment groups will be performed for the continuous change from baseline variable [REDACTED] for each defined time point separately, [REDACTED]

The [REDACTED] are described in section 10.1.3.

10.1.3. General Multiple Imputation Approach

The primary analysis approach for mRS and NIHSS efficacy endpoints will consider the multiple imputation (MI) of missing data [REDACTED]

This document is confidential.

[REDACTED]

[REDACTED]

[REDACTED]

This document is confidential.

10.1.4. Supportive analyses:

The main analysis will be repeated on the PP and Completers populations as supportive analyses.

10.2. Further Efficacy Endpoints and Analysis

10.2.1 Occurrence of recurrent stroke within 90 days after the 1st IP:

The number and percentage of subjects who have a recurrent stroke within 90 days after the 1st IP will be presented by treatment group on the observed ITT. The difference of the proportions between the treatment groups with the corresponding 95% CIs will be presented.

10.2.2. Montreal Cognitive Assessment (MoCA)

The MoCA total score and subscale will be summarized

This document is confidential.

[figure not shown]
10.2.3. Change of infarct volume [REDACTED] from Baseline by MRI/CTP

The absolute and percentage change from baseline of infarct volume in MRI or CTP examination will be presented [REDACTED] by treatment group on observed ITT. Comparisons between treatments will be performed on observed ITT [REDACTED]

10.2.4. The infarct volume [REDACTED] after the 1st IP by MRI/CTP [REDACTED]

A comparison between the treatment group [REDACTED]

10.2.5. Change of hypoperfusion lesion [REDACTED] from Baseline

The absolute and percentage changes from baseline in hypoperfusion lesion in perfusion-weight imaging MRI or CTP will be summarized [REDACTED]

This document is confidential.

10.2.6. Proportion of subjects with 90% reduction in hypoperfusion lesion [REDACTED]
[REDACTED] from Baseline:

The number and percentage of subjects showing 90% reduction in hypoperfusion lesion [REDACTED]
[REDACTED] will be summarized by treatment group. The difference of the
proportions between the treatment groups and the corresponding 95% CIs will be presented.
Comparisons between treatment groups will be made on the observed data using the Chi-square test
[REDACTED].

[REDACTED]

This document is confidential.

11. Safety

Safety analyses will be performed on the Safety population.

Safety will be assessed based on the incidence of AEs and changes in laboratory results, vital signs, and ECG parameters. For repeated safety assessments collected at scheduled time points, the last non-missing pre-dose value will be used as baseline, and the first non-missing value at each post-dose time points will be used in the analyses. However, all pre- and post-dose assessments including repeat assessments will be presented in data listings. Data collected at unscheduled visits will be included in data listings but will not be considered for analyses.

All safety summaries and analyses will be performed using observed data on the Safety population without imputation of any missing safety data.

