### 12.3 Vital Signs

Vital signs (body temperature, pulse rate, respiration rate, and systolic and diastolic blood pressure measurements) will be evaluated at the visits indicated in the Schedule of Assessments ([Table 1](#)). All vital signs will be measured after the subject has been resting in a supine position for at least 5 minutes. Blood pressure measurements are to be taken in the same arm for the duration of the study.

Vital sign measurements will be repeated if clinically significant or machine/equipment errors occur. Out-of-range blood pressure, respiration rate, or pulse rate measurements will be repeated at the Investigator's or designee's discretion. Any confirmed, clinically significant vital sign measurements must be recorded as AEs.

Body weight (without shoes) will be recorded at Screening (Visit 1) only. For subjects who cannot stand on a scale, bed weight measurement is allowed at the Investigator's or designee's discretion.

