#### **12.5 Electrocardiograms**

A 12-lead, resting ECG will be obtained at the visits indicated in the Schedule of Assessments ([Table 1](#)).

At Screening (Visit 1), the Investigator will examine the ECG traces for signs of cardiac disease that could exclude the subject from the study. An assessment of normal or abnormal will be recorded; if the ECG is considered abnormal, the abnormality will be documented on the eCRF. ECGs will be repeated if clinically significant abnormalities are observed or artifacts are present at the Investigator's or designee's discretion.

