8.2. Key Definitions

- Unless otherwise defined, baseline is defined as the last non-missing assessment prior to the first dosing.
- Study Day 1 is defined as the date on which a subject took the first dose of study drug**. Other study days are defined relative to Study Day 1.

For assessments occurring on Day 1 or after, Study Day will be calculated as (date of assessment – date of first dose + 1). For assessments occurring before Day 1, Study Day will be calculated as (date of assessment – date of first dose).

This document is confidential.

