11.2.6. Vital Signs

Vital signs (systolic blood pressure, diastolic blood pressure, pulse rate, respiratory rate, body temperature) will be summarized descriptively by parameter and visit. Similarly, changes from baseline will be summarized. Shift table will be presented at each post-baseline visit showing the number and percentage of subjects with normal, abnormal NCS or abnormal CS at baseline and post-baseline visit, where available. Vital signs data will be listed.

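### SAP Section 11 has no exception for readings repeated because of equipment error or artifact, so a stored faulty post-dose value is analysed and its valid repeat is only listed

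*SAP*

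**What the plan says.** SAP Section 11 (Safety) sets the selection rule for repeated safety assessments at scheduled time points. Before dosing, "the last non-missing pre-dose value will be used as baseline". After dosing, "the first non-missing value at each post-dose time points will be used in the analyses". SAP Section 8.2 agrees on the baseline side: "baseline is defined as the last non-missing assessment prior to the first dosing". Repeats are not lost, since Section 11 adds that "all pre- and post-dose assessments including repeat assessments will be presented in data listings".

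The protocol says why repeats are taken:

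- Section 12.3: "Vital sign measurements will be repeated if clinically significant or machine/equipment errors occur".
- Section 12.3, at the discretion of the investigator or designee: "Out-of-range blood pressure, respiration rate, or pulse rate measurements will be repeated".
- Section 12.5, also with discretion: "ECGs will be repeated if clinically significant abnormalities are observed or artifacts are present".

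The selected values feed change-from-baseline summaries for vital signs (SAP 11.2.6) and ECG (SAP 11.2.7). They also feed shift tables, which compare each later visit with the pre-dose grading. For vital signs: "Shift table will be presented at each post-baseline visit showing the number and percentage of subjects with normal, abnormal NCS or abnormal CS". For ECG, the table uses the overall interpretation. The visible text of SAP Section 11 does not treat a reading documented as equipment error or artifact differently from any other.

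**The concern.** A pre-dose repeat displaces the reading that prompted it, while a post-dose repeat does not. This has two consequences.

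First, where the site repeated a post-dose measurement because the device failed or the trace was contaminated, the rule analyses the failed measurement and leaves the good one in a listing.

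Second, repeats follow abnormal readings. Taking the last value at baseline removes some unconfirmed abnormal readings there, and taking the first value post-dose leaves them in. Within each arm, more subjects will then appear to go from normal to abnormal than the reverse, even if nothing has changed.

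At stake is the readability of the vital-sign and ECG tables, which SAP Section 11 names as part of the safety assessment. A reader who looks at one arm's shifts alone could take them for a drug effect.

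**Working it through.** The documents state no figure on this point, so there is nothing to reproduce. The selection rules and repeat triggers come from the sections cited above. All rates, means, SDs and cut-offs below are assumptions.

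**1. One faulty reading, followed by a valid repeat at the same time point**

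| Where it occurs | Analysed | Listed only |
|---|---|---|
| Pre-dose | valid repeat | faulty reading |
| Post-dose | faulty reading | valid repeat |

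This requires the faulty value to be stored as non-missing. The plan to list repeat assessments suggests that both values are kept, but the data-entry instructions are not in the documents. A numeric fault reaches the change-from-baseline summary directly. It reaches a shift table only if that record was graded abnormal.

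**2. Selective repeats, no true change**

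Let q be the probability that a single reading is abnormal but would not persist, and r the probability that an abnormal reading is repeated.

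- Abnormal on the first reading: q
- Abnormal on the last reading: b = q(1 − r) + r·q²
- Normal-to-abnormal: (1 − b)·q
- Abnormal-to-normal: b·(1 − q)
- Net apparent worsening: q − b = r·q·(1 − q), which is positive whenever r > 0 and 0 < q < 1

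For q = 5% and r = 1, b = 0.05² = 0.0025. Worsening is 0.9975 × 0.05 = 4.99 per 100 and improvement is 0.0025 × 0.95 = 0.24 per 100. The net is 0.05 × 0.95 = 4.75 per 100.

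| q | r | Worsen per 100 | Improve per 100 |
|---|---|---|---|
| 1% | 0.5 | 0.99 | 0.50 |
| 1% | 1 | 1.00 | 0.01 |
| 5% | 0.5 | 4.87 | 2.49 |
| 5% | 1 | 4.99 | 0.24 |
| 10% | 0.5 | 9.45 | 4.95 |
| 10% | 1 | 9.90 | 0.90 |

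With the first reading at both ends and q = 5%, both directions give 0.95 × 0.05 = 4.75 per 100.

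**3. Separating faulty readings from ordinary variation**

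This is a simulation of 2 million subjects with a systolic-pressure-like variable and no drug effect. Mean 145, between-subject SD 15, within-subject SD 8, cut-off 160, every reading above the cut-off repeated.

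| Rule | Device errors | Worsen | Improve | Mean change |
|---|---|---|---|---|
| SAP (last pre, first post) | none | 10.02% | 2.82% | +1.03 mmHg |
| SAP (last pre, first post) | 2%, each +40 | 11.36% | 2.84% | +1.75 mmHg |
| First at both ends | none | 7.20% | 7.21% | +0.01 mmHg |
| Last at both ends | none | 4.36% | 4.35% | +0.01 mmHg |

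The faulty readings themselves account for 11.36 − 10.02 = 1.34 points of worsening and 1.75 − 1.03 = 0.72 mmHg. As a plausibility check, 2% of +40 is 0.8 mmHg. The rest comes from valid readings that were selectively repeated. Over within-subject SDs of 5 to 12, the SAP rule ran from 6.45% v 1.94% (SD 5, no errors) to 15.55% v 3.88% (SD 12, 2% errors).

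Other assumptions move the size considerably. With mean 150, SDs 18 and 8, a cut-off of 180 and no device errors, the shifts are 3.8% v 1.0% with a mean rise of 0.4 mmHg. With within-subject SD 10 and a cut-off of 170 they are 9.4% v 2.6% with a rise of 1.2 mmHg. The upward mean depends on only high readings being repeated. If low readings are repeated too, the mean effects partly cancel, but the shift counts do not.

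**4. Between arms**

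With q = 5%, r = 1 and 100 subjects per arm (about 200 randomised 1:1), the simulated mean difference in worsening proportion was −0.0004. A 5% chi-square test rejected in 4.4% of trials. The treatment comparison is not biased.

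**The case against.** The strongest reply is that the first post-dose value is a sensible safety convention, and much of that stands. Several repeat triggers are genuine abnormal findings, and the protocol nowhere says that a repeat replaces the reading before it. The first reading is unselected; the last reading, where only abnormal values are re-measured, is not. In the example with mean 150 and cut-off 180, the single-reading abnormal rate is P(Z > 30/√(18² + 8²)) = 6.4%. That is the honest rate, and the 3.6% under a last-value rule is the selectively lowered one. Protocol Section 5.2.1 also reports blood-pressure falls and heart-rate rises in animals, which in monkeys resolved within hours. A blanket last-value rule could replace such a transient change with the recovered repeat.

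It is also fair that the planned vital-sign and ECG shift tables use graded interpretations rather than a numeric cut-off, so the percentages above illustrate a mechanism and do not forecast those tables. Repeats of out-of-range values are discretionary, which pulls r below 1.

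A reader might infer more than the documents support: that most repeated readings are known to be wrong, that the rule creates a false signal against the drug, or that the primary safety result is compromised. The first fits only the equipment-error and artifact subset. The second fails because blinding and randomisation make the effect similar in both arms. The third fails because the primary endpoint is related adverse events, and the secondary safety endpoints in SAP Section 5.2 are intracranial haemorrhage, mortality and adverse events; none uses this rule.

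What the reply does not answer is why a reading documented as a device fault or artifact should be analysed ahead of its valid repeat.

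**Conclusion.** The point holds in a limited form. As written, SAP Section 11 lets a documented faulty post-dose reading, if stored, into the vital-sign and ECG summaries while its valid repeat is only listed. The opposite selection rules at the two ends also produce some apparent within-arm worsening. The direction of the shift imbalance follows from the rule whenever abnormal readings are sometimes repeated and some do not persist. The size is unknown: the modelled net excess runs from about 0.5 per 100 (q = 1%, r = 0.5: 0.99 − 0.50) to 9 per 100 (q = 10%, r = 1: 9.90 − 0.90), all on assumed rates.

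The treatment difference is not biased, all comparisons are declared descriptive (SAP 8.1), and the primary endpoint is untouched. This is a cheap improvement to supporting safety tables, not a threat to the trial's conclusions.

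**What to change.** In SAP Section 11, before the selection rule is applied at baseline and at each post-dose time point:

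- Exclude any reading documented as equipment error or artifact, and use the valid repeat from the same time point. State that such a repeat counts for the scheduled time point even if it was entered on an unscheduled page; otherwise the exclusion of unscheduled data would leave a gap.
- Otherwise keep the first valid post-dose reading, so that real transient changes are not replaced.
- Keep every reading in the listings.
- Add a note that selective pre-dose repeats can inflate within-arm shifts, so the tables should be read against placebo. Alternatively, add a sensitivity summary using the first valid scheduled reading at both ends, which restores symmetry (7.20% v 7.21% in the model above).

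The cost is one SAP sentence and one derivation flag, with no new data. The downside is reliance on the site's documented reason for the repeat, so the flag should be set before unblinding. The first step removes only the faulty-reading component; the residual imbalance from selective repeats is handled by the note or the sensitivity summary.
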